7.4. Examination of Subgroups

A pre-specified sub-group analysis will be performed on subjects with pain scores ≥ 5 as well as subjects with A1C above and below 8.5.

8. SUBJECT ACCOUNTING AND STUDY DISPOSITION

A complete accounting of subject participation in the study will be presented in Table 14.1.1 entitled *Subject Accounting and Final Study Disposition*. The Level 1 table layout will be used to present these results. The purpose of this table is to provide an accounting of subjects from their entrance into the study through the final visit and to account for subject evaluation in major analyses of safety and efficacy, including reasons for early study termination. The table will display the number and percentage of subjects who:

- were consented
- were screened
- were run-in failures
- are included in the ITT Population
- are included in the *Per protocol Population*
- completed the study

In addition, the reason for early study termination will be summarized separately using the number and percentage of subjects within each table column for each reason.

Listing 16.2.1 entitled *Subject Disposition* supports Table 14.1.1. This listing will be sorted by subject number and will contain the reason for discontinuation (if applicable), along with the date and last study visit attended.

Listing 16.2.2.1 entitled *Inclusion Criteria* displays the data from the Inclusion Criteria case report form (CRF). The data will be displayed for each subject and for each inclusion criterion. The listing will be sorted by subject number.

9. BASELINE SUBJECT DATA

9.1. Baseline Demographic Factors

All subjects in the *ITT Population* will be included in Table 14.1.2 entitled *Summary of Baseline Demographics and Subject Characteristics*. The Level 1 table layout will be used to present these results. This table summarizes the subject population with respect to gender, age in years at the time of entry into the study, race, ethnicity, height (cm), weight (lbs), calculated body mass index (BMI), total foot thickness (plantar surface to mid-dorsal surface on the right and left foot) [cm], venous insufficiency classification, diabetes type, HbA1c, foot length (cm), foot width (cm), and shoe size. Data collected using a continuous scale will be summarized using descriptive statistics. Data collected using a categorical scale will be presented using counts and percentages. The supportive data for Table 14.1.2 will be presented in Listing 16.2.4.1 entitled *Subject Demographics and Subject Characteristics*. This listing will be sorted by subject number

9.2. Screening and Baseline Assessments

The purpose of these assessments is to determine the severity of the disease for each subject. Outcomes may be assessed on baseline disease severity by adding these results as a covariate to the model for analysis. The parameters to be summarized are listed below; the method of summarization will be predicated on the scale used for each parameter (continuous or categorical). Results will be presented using the *Level 1* display for the *ITT Population*.

- Pain Score Assessment (NPRS)
- Toronto Clinical Neuropathy Scoring System (TCNSS)
- Ankle-Brachial Index & Assess Venous Insufficiency
- Quantitative Sensory Test (QST)
- Sural Nerve Conduction Velocity and Amplitude (NCS)
- Measure HbA1c
- Work Productivity and Activity Impairment Questionnaire (WPAIQ)
- Skin Perfusion Pressure (SPP)
- NeuroQoL Questionnaire
- Biopsy measurements

All subjects in the ITT / Safety population will be included in Table 14.1.3 entitled *Summary of Screening and Baseline Assessments* (ITT / Safety population). The supportive data for Table 14.1.3 will be presented in Listing 16.2.4.2 entitled *Screening and Baseline Assessments*. This listing will be sorted by patient number.

Screening assessments will be presented in the following tables:

 Table 14.1.2
 Summary of Baseline Demographics and Subject Characteristics

 Table 14.1.3
 Summary of Screening and Baseline Assessments

9.3. Physical Examination

There will be 5 body systems assessed as either normal or abnormal in the physical examination:

- General Appearance
 - Normal Abnormal
- Cardiovascular
 - Normal Abnormal
- Musculoskeletal
 - Normal Abnormal
- Extremities/Skin
 - Normal Abnormal
- Neurological
 - o Normal Abnormal (Other abnormalities other than DPN will be noted)
- Other, specify:

Results will be presented using the *Level 1* display for the *ITT Population*. Results will be summarized in Table 14.1.4 entitled *Summary of the Physical Examination Results*. The supportive data for this table will be presented in Listing 16.2.4.3 entitled *Physical Examination Results*. This listing will be sorted by subject.

9.4. Medical and Surgical History

The medical and surgical history will be coded for each subject. Results will be presented based on the reported history using the *Level 1* display for the *ITT Population*. Results will be summarized based on the body system description and presented in Table 14.1.5 entitled *Summary of Medical and Surgical History*. The subjects will be summarized using counts and percentages for those subjects who had a pre-study medical history. The supportive data for this table will be presented in Listing 16.2.4.4 entitled *Medical and Surgical History*. This listing will be sorted by subject.

10. STUDY DEVICE ACCOUNTABILITY AND TREATMENT

This section will describe the summarization and analysis of the administration of the treatment with the Provant device (active and sham).

10.1. Treatment Administration and Accountability

A summary of treatment sessions with the study device will be presented in Table 14.2.1 entitled Summary of Treatment with the Study Device (Active and Sham) and Table 14.2.2 entitled Summary of Compliance with the Study Device (Active and Sham). The number and percentage of subjects who undergo treatment will be calculated and summarized using counts and percentages. The number of completed treatment sessions, and the number of treatment sessions initiated but not completed will be calculated and summarized using counts and percentages. Percent compliance will be calculated, including the number of subjects with >=70% compliance. Listing 16.2.5.1 entitled Study Device – Application and Accountability will contain all of the recorded treatment information; this listing will be sorted by subject number and relative study day.

11. EFFICACY EVALUATIONS

The primary endpoint for the study is the change from baseline in the NPRS score at 4 months. The primary hypothesis to be tested is presented below:

Ho: μ (Change in NPRS score at 4 months / PEMF group) = μ (Change in NPRS score at 4 months / sham group)

Ha: μ (Change in NPRS score at 4 months / PEMF group) $\neq \mu$ (Change in NPRS score at 4 months / sham group)

To compare the absolute change in pain from baseline to 4-months, the intra-patient change will be calculated and serve as the dependent variable in the analysis. The baseline pain score will be introduced in the model as a covariate. Clinical site will be added to the model to assess poolability of the data across sites. Interaction between clinical site and treatment will be evaluated using a type 1 error rate of 10%. A Mixed Models with Repeated Measures (MMRM) analysis comparing results across all time-points will also be performed, adjusted for the baseline value, week, treatment by week interaction and the effect of the patient.

The primary efficacy endpoint will be summarized and reported using the Level 3 table design. Results will be presented in Table 14.4.1.1 entitled Summary of the Pain Intensity by Randomized Treatment Assignment and Time (ITT Population)

Listing 16.2.8.1 entitled *Pain Intensity by Randomized Treatment Assignment and Time* will contain all of the recorded information; this listing will be sorted by subject number and relative study day.

A list of additional summary tables is presented in the table below.

Table	Description
14.4.1.1.1	Kaplan-Meier Estimates for the First Week where a Mean Reduction of 2 Points or a 30% Reduction from Baseline in the NPRS is Observed
14.4.1.1.2	Summary of the Pain Intensity Categorized by Success (>=30% reduction from baseline) by Randomized Treatment Assignment and Time
14.4.1.1.3	Summary of the Pain Intensity Categorized by Success (>=2 point reduction from baseline) by Randomized Treatment Assignment and Time
14.4.1.1.4	Summary of the Pain Intensity Categorized by Success (>=2 point reduction or 30% reduction from baseline) by Randomized Treatment Assignment and Time

Table	Description
14.4.1.2	Summary of the NeuroQoL Results by Question, Randomized Treatment Assignment and Time
14.4.1.2.1	Summary of the Efficacy Endpoints by Randomized Treatment Assignment and Time - NeuroQol (Weighted) Domain 1: Pain
14.4.1.2.1a	Summary of the Efficacy Endpoints by Randomized Treatment Assignment and Time - NeuroQol (Unweighted) Domain 1: Pain
14.4.1.2.2	Summary of the Efficacy Endpoints by Randomized Treatment Assignment and Time - NeuroQol (Weighted) Domain 2: Lost/reduced feeling
14.4.1.2.2a	Summary of the Efficacy Endpoints by Randomized Treatment Assignment and Time - NeuroQol (Unweighted) Domain 2: Lost/reduced feeling
14.4.1.2.3	Summary of the Efficacy Endpoints by Randomized Treatment Assignment and Time - NeuroQol (Weighted) Domain 3: Diffuse sensory-motor symptoms
14.4.1.2.3a	Summary of the Efficacy Endpoints by Randomized Treatment Assignment and Time - NeuroQol (Unweighted) Domain 3: Diffuse sensory-motor symptoms
14.4.1.2.4	Summary of the Efficacy Endpoints by Randomized Treatment Assignment and Time - NeuroQol (Weighted) Domain 4: Restrictions in activities of daily living
14.4.1.2.4a	Summary of the Efficacy Endpoints by Randomized Treatment Assignment and Time - NeuroQol (Unweighted) Domain 4: Restrictions in activities of daily living
14.4.1.2.5	Summary of the Efficacy Endpoints by Randomized Treatment Assignment and Time - NeuroQol (Weighted) Domain 5: Disruptions in social relationships
14.4.1.2.5a	Summary of the Efficacy Endpoints by Randomized Treatment Assignment and Time - NeuroQol (Unweighted) Domain 5: Disruptions in social relationships
14.4.1.2.6	Summary of the Efficacy Endpoints by Randomized Treatment Assignment and Time - NeuroQol (Weighted) Domain 6: Emotional distress
14.4.1.2.6a	Summary of the Efficacy Endpoints by Randomized Treatment Assignment and Time - NeuroQol (Unweighted) Domain 6: Emotional distress
14.4.1.3	Summary of the Skin Perfusion Pressure Results by Randomized Treatment Assignment and Time
14.4.1.4	Summary of the Nerve Conduction Results by Randomized Treatment Assignment and Time
14.4.1.5	Summary of the QST Results by Randomized Treatment Assignment and Time
14.4.1.6	Summary of the Work Productivity and Activity Impairment Questionnaire (WPAIQ) by Visit and Randomized Treatment Assignment
14.4.1.7	Summary of the Patient Global Impression (PGI) by Visit and Randomized Treatment Assignment
14.4.1.8	Summary of Treatment Satisfaction by Visit and Randomized Treatment Assignment
14.4.1.10	Summary of the Toronto Clinical Neurpathy Scoring System by Randomized Treatment Assignment and Time

12. SAFETY

The following sections describe how the safety endpoints will be analyzed.

12.1. Adverse Events

12.1.1. Missing and Partial Adverse Event Dates

The start dates for AEs are important for the:

- 1. Treatment emergent algorithm.
- 2. The designation of unique AE occurrences.

Completely missing or partially missing adverse event onset dates will be imputed as follows after due diligence to obtain accurate adverse event information has failed.

If the AE start date is completely missing then the AE will be considered treatment-emergent unless it can be determined that the AE end date occurred prior to the start of the study. If this is the case, the AE will not be considered treatment-emergent.

If the adverse event start date is partially missing and the partial date is not sufficient to determine if the event occurred after the start of the study, then the AE will be considered treatment-emergent unless it can be determined that the AE end date occurred prior to the start of the study.

12.1.2. Summaries of Adverse Events

All summaries of AEs will be based on treatment-emergent AEs and presented using the Level 2 table designs. Adverse events will be coded using the system organ class and preferred term. The number and percentage of subjects experiencing AEs will be summarized by system organ class and preferred term. Summaries by maximum severity and relationship to the study device (active or sham) will also be provided. Serious adverse events and AEs leading to discontinuation from the study will be presented by reported adverse event term.

12.1.2.1. Summary of Adverse Events by Reported Adverse Event Term

Table 14.3.1.1 entitled Summary of Adverse Events by Randomized Treatment Assignment, System Organ Class, and Preferred Term will contain the primary presentation of the AE data. This table will be prepared without regard to causality or relationship to the study device. The number and percentage of subjects experiencing an adverse event will be displayed by treatment (active or sham). Reported adverse event terms will be displayed alphabetically. The incidence of AEs will be summarized using counts and percentages.

12.1.2.2. Assessment of Severity

Table 14.3.1.2 entitled Summary of Adverse Events by Reported Adverse Event Term and Severity will provide the presentation of AEs with respect to the severity or intensity of the event using the scale presented in the protocol. Subjects with multiple occurrences of the same reported adverse event term within the same period will be summarized at the maximum severity

November 7, 2018

reported for that AE. The number and percentage of subjects experiencing AEs for each coded adverse event term will be displayed by study device (active or sham).

12.1.2.3. Assessment of Relationship to the Study Device

Table 14.3.1.3 entitled Summary of Adverse Events by Randomized Treatment Assignment and Relationship to the Study Device will present the adverse events by the relationship to the study device. The categories for assessment of the relationship to the study device are defined in the protocol. Subjects with multiple occurrences of the same coded adverse event term will be summarized using the event with the strongest relationship to the study device (active or sham). The number and percentage of subjects experiencing each reported adverse event term will be displayed by study device (active or sham).

Listing 16.2.7.1 entitled *Adverse Events* will provide supportive data for Tables 14.3.1.1 through 14.3.1.3 and will be sorted by subject number and relative day.

12.1.2.4. Summary of Adverse Events Leading to Discontinuation

Results will be presented in Table 14.3.1.4 entitled *Summary of Adverse Events Leading to Discontinuation of Treatment with the Study Device* by the coded adverse event term. The structure of the table will follow Table 14.3.1.1. Listing 16.2.7.3 entitled *Adverse Events Leading to Discontinuation of Treatment* will display all treatment-emergent AEs resulting in an action taken of "Discontinued".

12.1.2.5. Summary of Serious Adverse Events

Results will be presented in Table 14.3.2 entitled Summary of Serious Adverse Events by Randomized Treatment Assignment, System Organ Class, and Preferred Term. The structure of the table will follow Table 14.3.1.1. Listing 16.2.7.2 entitled Serious Adverse Events will present the AEs coded as serious. The format of Listing 16.2.7.2 will be similar to that of Listing 16.2.7.1 with the exception that the column indicating whether or not the AE was serious will be removed as all AEs in this listing will be SAEs.

A complete list of the safety summary tables is presented in the table below.

Table	Description
14.3.1.1	Summary of Adverse Events by Randomized Treatment Assignment, System Organ Class, and Preferred Term
14.3.1.2	Summary of Adverse Events by Reported Adverse Event Term and Severity
14.3.1.3	Summary of Adverse Events by Randomized Treatment Assignment and Relationship to the Study Device
14.3.1.4	Summary of Adverse Events Leading to Discontinuation from the Study
14.3.2	Summary of Serious Adverse Events by Randomized Treatment Assignment, System Organ Class, and Preferred Term

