	 Secondary Endpoints: Percentage of patients who have either a 2 point or 30% reduction in NPRS at 4 Months. Time to 30% or 2-point reduction in NPRS, whichever comes first at 4 Months. Change in neuropathy related quality of life (NeuroQoL) between baseline and end of treatment at 4 Months. Changes in Skin Perfusion Pressure from baseline to end of treatment at 4 Months. Changes in Nerve Conduction Studies of Velocity and/or Amplitude between baseline and end of treatment at 4 Months. Changes in Quantitative Sensory Testing between baseline and end of treatment at 4 Months. Changes in Patient Global Impression at 4 Months.
	 Exploratory Endpoints: Changes in WPAIQ Changes in intraepidermal nerve fiber density (IENFD) at the distal thigh. Changes in IENFD at the distal leg. Evaluation of the NPRS, NCS and NeuroQoL during Part B will be considered avalantees.
Safety Endpoints	 Adverse events, serious adverse events Unanticipated adverse device effects

Γ

Study Device	The study device is the PROVANT [®] Therapy System. The active device will deliver dual field pulsed electromagnetic field energy in the radiofrequency range. The active treatment and inactive sham devices will be identical in appearance and all other physical characteristics in order to maintain the blinding of the treatment. Each device will be identified with a unique kit number.
Inclusion/Exclusion	Inclusion Criteria
	 Subject has documented Type 1 or Type 2 diabetes mellitus according to the ADA criteria (Appendix B).³³ Subject has daily pain attributed to symmetrical lower extremity diabetic peripheral neuropathy for at least 6 months prior to screening, as confirmed by score of ≥ 6 on the Toronto Clinical Neuropathy Scoring System. Subjects' average lower extremity pain related to diabetic peripheral neuropathy over the preceding 24 hours is ≥4 and <9 based on the 11-point NPRS (0-10) at the Screening Visit. Subject age is greater than or equal to 22 years and less than 80 years of age. Subject has an HbA1c ≤10% at Screening or within 3 months of Screening. Subject has an ankle-brachial index (ABI) of ≥0.8 to ≤1.3. If the subject has incompressible vessels, a toe brachial index of 0.8 to 1.3 is required. These adequate lower extremity studies are with no documented intermittent claudication.
	9. Subject walks independently with or without assistive devices, and does not require a wheel chair.

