7.3 Adverse Events

All summaries of adverse events will be based on treatment-emergent adverse events. Adverse events will be provided in a listing. The number and percentage of subjects experiencing adverse events will be summarized. Summaries by maximum severity and relationship to the study device (active or sham) will also be provided. Serious adverse events and adverse events leading to discontinuation from the study will be presented. Treatment-related adverse events will be defined as adverse events with investigator assessment of related or possibly related. In summaries of adverse events by severity and relationship to study device, patients reporting multiple episodes will be counted once under the worst severity and the strongest relationship, respectively. Serious adverse events will also be presented by relationship to treatment. The number of patients with at least one adverse event will be tabulated for each treatment group. The number of adverse events for each treatment group will also be tabulated.

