3.1.2. Safety Endpoints

Safety will be assessed through review of Adverse Event (AE) reports and unanticipated adverse device effects. Safety outcomes will be assessed at the interim visits and the end of study visit.

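### The SAP's safety tables do not identify UADEs by arm or show SAEs by device relationship, and the severity table mixes reported and coded terms

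*SAP*

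**What the plan says.** **Endpoints.** The protocol synopsis lists, under safety endpoints and separately from adverse events, "Unanticipated adverse device effects". SAP 3.1.2 agrees: "Safety will be assessed through review of Adverse Event (AE) reports and unanticipated adverse device effects".

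**Planned tables.** SAP 12.1.2.5 states "A complete list of the safety summary tables is presented in the table below" and names five: 14.3.1.1 (adverse events by system organ class and preferred term), 14.3.1.2 (by severity), 14.3.1.3 (by relationship), 14.3.1.4 (leading to discontinuation) and 14.3.2 (SAEs by system organ class and preferred term).

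**SAEs and relationship.** Protocol 7.3 says "Serious adverse events will also be presented by relationship to treatment". For Table 14.3.2, SAP 12.1.2.5 says "The structure of the table will follow Table 14.3.1.1", and SAP 12.1.2.1 says of that template: "This table will be prepared without regard to causality or relationship to the study device".

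**Row unit.** SAP 12.1.2 codes events to system organ class and preferred term, but also says "Serious adverse events and AEs leading to discontinuation from the study will be presented by reported adverse event term". Table 14.3.1.2 is titled "Summary of Adverse Events by Reported Adverse Event Term and Severity". Its text in SAP 12.1.2.2 takes the maximum severity within the reported term and then displays counts per coded term.

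**The concern.** A safety endpoint named in both documents should have a planned result by arm, even if that result is zero. Without one, a reader of the study report cannot tell from the summary tables whether no UADE occurred or whether none was separated out.

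Relationship matters most for serious events. If SAEs are summarised without it, the attribution promised in the protocol has to be rebuilt case by case.

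The row unit is a smaller matter, but it changes counts. Where the level at which a maximum is taken differs from the level at which rows are displayed, the rule to count each subject once no longer holds. Two programmers following the same section could then produce different severity tables.

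**Working it through.** No sample size, power or event figure is involved. The check compares the endpoints and commitments with the outputs named in the SAP.

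**1. UADEs.** Among the five tables, the number covering UADEs is 0. The further tables in SAP 12.2 and 12.3 concern analgesic and rescue medication, blinding, the Toronto score and HbA1c. The listings named in section 12 cover adverse events, SAEs, discontinuations and medications, and none mentions a UADE flag. Protocol 11.3 defines a UADE as serious, so two cases follow:
- A UADE that is a treatment-emergent adverse event enters Table 14.3.2 and Listing 16.2.7.2, without being marked as a UADE.
- The definition also takes in other unanticipated serious problems tied to the device that bear on subjects' rights, safety or welfare. If such a problem is not an adverse event, no named output receives it.

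**2. SAEs by relationship.** Among the five tables, the number crossing seriousness with relationship is 0. Table 14.3.2 has seriousness without relationship, because it inherits the layout of 14.3.1.1. Table 14.3.1.3 has relationship without seriousness. The two cannot be combined to recover related SAEs, because 14.3.1.3 keeps only the strongest relationship per subject and term, whether or not that event was the serious one.

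**3. Row unit.** Usage by place in the SAP:

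| Place | Reported term | Coded or preferred term |
|---|---|---|
| 7, Level 2 shell | row label | none |
| 12.1.2 | SAEs and discontinuation events | coding rule, overall incidence |
| 12.1.2.1, Table 14.3.1.1 | terms displayed | title |
| 12.1.2.2, Table 14.3.1.2 | title, maximum-severity rule | counts displayed |
| 12.1.2.3, Table 14.3.1.3 | counts displayed | strongest-relationship rule |
| 12.1.2.4, Table 14.3.1.4 | none | table rows (against 12.1.2) |
| 12.1.2.5, Table 14.3.2 | none | title (against 12.1.2) |

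A constructed case shows the consequence for Table 14.3.1.2. One subject has two events with different wordings that code to the same preferred term, one mild and one moderate. The maximum is taken within each wording, so both survive. Displayed by coded term, the subject counts once as mild and once as moderate: two entries in one row. Protocol 7.3 gives one entry, moderate. In Table 14.3.1.3 the mismatch runs the other way, with the rule at coded level and the display at reported level.

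**The case against.** The strongest reply is that little information is lost. UADEs that are adverse events are counted by arm in Table 14.3.2. SAP 7 says all study data will be listed. The SAE listing resembles the adverse event listing that supports the relationship table, so relationship could be read from it. Protocol 7.3 asks for SAEs to be presented by relationship without requiring a table, and it asks for no UADE table. Protocol 10 and 11.3 provide separately for UADE evaluation and reporting. The index of tables and listings is a separate file (SAP 15) that is not among the documents and may name more listings.

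Much of this stands, and it rules out two stronger readings. A reader might infer that UADEs would go unreported altogether. The documents do not support that for UADEs that are treatment-emergent adverse events, which are serious by definition and so reach the SAE outputs. A reader might also infer that severity is to be tabulated by verbatim term, scattering one device reaction over many rows. SAP 12.1.2.2 itself displays counts by coded term, so the finding there is a contradiction and not a settled verbatim display.

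The reply does not supply identification of UADEs, an output for non-AE device problems, or any statement of how the Protocol 7.3 commitment on SAEs is met. The unseen index is of limited help for tables, since the SAP calls its own list complete.

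**Conclusion.** The point holds in three parts.

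- UADEs, a stated safety endpoint, have no output that identifies or counts them by arm.
- SAEs by device relationship, promised in Protocol 7.3, have no summary in the SAP, and the planned tables cannot be combined to give one.
- The row unit for adverse event tables is contradictory. As written, the severity rule allows one subject to be counted at two severities under one coded term, against Protocol 7.3.

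The size is 0 of 5 listed tables for each of the first two parts, and mixed or conflicting usage in the Level 2 shell and from 12.1.2 to 12.1.2.5 for the third. How many subjects the severity rule would affect cannot be derived from the documents. The conclusion takes the SAP at its word that its list of safety tables is complete. It concerns safety reporting in Part A and does not touch the primary efficacy analysis. It should be corrected before the tables are programmed.

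**What to change.** 1. Add a table of UADEs by arm with a supporting listing. Show zeros explicitly, which needs an exception to the SAP 7 convention that drops all-zero rows. Include serious device problems that meet the Protocol 11.3 definition but are not adverse events.
2. Add a table of SAEs by relationship to the device and by arm, using the protocol's causality categories.
3. State system organ class and preferred term as the row unit, and as the level at which the maximum-severity and strongest-relationship rules apply. Make this change in the Level 2 shell in SAP 7 and in every section from 12.1.2 to 12.1.2.5, including the title of Table 14.3.1.2.
4. Update the list in 12.1.2.5 and the separate table index to match.

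The cost is two small added tables and one re-keyed table. Seriousness, causality, severity, coding and UADE reports are already required by the protocol, so no new data collection is needed.
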